## DATA MANAGEMENT

### 26.0 Data Collection\*

**26.1** *Provide a general description of the types or categories of data that will be collected during the study (e.g., lab test results, procedure outcomes, length of stay, questionnaires, surveys).*

We will collect survey data about the participants well-being, experiences with lactation, lactation goals, and history of lactation practices.

We will also collect device data from Willow Inc. that measures timing of pumping, length of pumping, and estimated volume.

*Describe the source of the data and how that data will be obtained (e.g. electronic medical record, previous research study, clinical database, surveys/questionnaires).*

We will collect this data via an entry survey, a monthly survey for the duration of pumping, and an exit survey. We will receive the device data from Willow using the device serial numbers to link with participant data.

**26.2 Sensitive Data:** *If collecting or accessing sensitive data which may pose legal, economic, or reputational harm, please specify here.*

None of the data we are collecting should pose legal, or economic harm. Participants may feel if their lactation goals are not met, that the data could pose reputational harm. Therefore we will ensure data is deidentified immediately when downloaded from RedCap. And stored on password protected computer and cloud storage devices.

•	

## 27.0 Adverse Events and Unanticipated Problems\*

**27.1 Monitoring:** *Describe the process for monitoring participants and data to identify adverse events and other unanticipated problems.*

On each monthly survey, we are asking about barriers that they may be experiencing. If the participant responds to this question, their response will be sent as an auto-notification to the site coordinator to review and take action as appropriate to protect and support the participant.

**27.2 Reporting:** *Confirm Policy 5.11 Reportable Events of the CM Research Program Policies and Procedures will be followed in regards to reporting adverse events and other unanticipated problems to the CM IRB. If deviating from, or expanding upon this policy, explain why the approved policy would not suffice for this study and the rationale for deviating/expanding.*

We will follow policy 5.11 Reportable Events and report adverse events or other unanticipated problems to the CM IRB.

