## STUDY INFORMATION

### 1.0 Study Summary\*

### 2.0 Objectives\*

#### 2.1 Purpose, specific aims or objectives: *Describe the purpose, specific aims, or objectives. If more than one objective be sure to list separately.*

This is a post-market study to provide breast pumps to residents at a pediatric academic medical center as an additional layer of support in reaching lactation goals. Residents that do not have flexible break times and/or reliable close and secure pumping space face barriers to reaching their lactation goals. Wearable pumps provide users autonomy and flexibility regarding their pumping schedules. These devices are not covered as a "free" breast pump through most insurance companies and, while discounted, are often still at a higher price point for most new parents. By providing these for free to users, we expect to see the institutions' metrics regarding duration of pumping and satisfaction with meeting goals will be higher than national metrics. In partnership with Willow, our institution will provide free pumps to individuals as part of a study including participant consent.

Among medical residents and fellows during the study window of 3 years (one year providing devices and up to three years collecting data, tracking users through end of pumping experience), who have delivered a baby. Does access to a wearable Willow pump improve lactation experience and meeting goals regarding duration of pumping/providing milk?

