### **Residents/Fellows and Physicians**

This training cohort consists of women of "peak" reproductive age, as defined by the American College of Obstetrics and Gynecologists (ACOG). ACOG states that in the U.S., "peak" reproductive age for women begins in late teens up to age 30 when fertility rates begin to decline. By age 45, natural pregnancy is unlikely and associated with higher risks for most women. While residents face the same barriers as other working mothers (e.g., inadequate space, support, and time), there are unique challenges for this group. Residents have training limitations to length of allowed parental leave outlined by their specialty boards (most boards only allow 6-8 weeks). Longer leave may result in the following situations: (1) a delay in receiving board certification; (2) a delay in

graduation, having to extend training; and (3) an impact on their career options post-training. Since these residents are considered trainees, they are also beholden to their training program schedule, supervising faculty expectations, and team structure in the healthcare setting.

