### 4.2 *Describe any primary or secondary safety endpoints.*

Individuals may also determine to end study participation based on the recommendation of their primary care physician.

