## SHORT TITLE: Lactation at Work

- *List the names of each instrument (survey, questionnaire, test, etc). Upload copies of any surveys, psychometric tests, or other instruments that will be administered for research purposes in the myIRB application, Other Attachments section.*

INTAKE SURVEY – expectation and goals for lactation experience, demographics and knowledge of lactation from previous experiences.

MONTHLY SURVEY – changes to lactation practices, current volume, frequency and satisfaction.

OUTTAKE SURVEY – final experience input, expectations vs reality, total length of time pumping and providing milk

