## 15.0 Risks to Participants\*

**15.1** *List the research risks. Research risks are any potential physical, psychological, social, legal, privacy, confidentiality risks or economic harms that may come from participating in the study. This does not include the risk of any procedures conducted as part of standard care.*

- *Where applicable, describe the probability, magnitude, duration, and reversibility of the risks.*
- *Describe the measures taken to minimize these risks as this will be useful for the IRB in making their risk/benefit determination.*
- *If collecting or accessing sensitive data which may pose legal, economic, or reputational harm, describe this risk in detail.*

**15.2** *Indicate whether the researchers believe the risks involved in this study are minimal, or if the study poses greater than minimal risk of harm to participants.*

**15.3** *If applicable, indicate which activities may have risks to the participants that are currently unforeseeable.*

**15.4** *If applicable, indicate which activities may have risks to an embryo or fetus, should the participant be or become pregnant.*

**15.5** *If applicable, describe risks to others who are not participants (e.g. pregnant partner of a male participant)*

There is minimal risk to participants other than normally occurring risks when pumping milk. These include low supply, infection, or stressors that can lead to individual's cessation of pumping. The study team will work to provide education on the device and access to lactation education to minimize risk.

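### Section 27.1 identifies adverse events through one voluntary monthly question about barriers, and no described survey item asks about infection, a risk the protocol itself names

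*Protocol*

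**What the plan says.** Section 27.1 has to describe how participants and data are monitored for adverse events. Its answer is the monthly item, "On each monthly survey, we are asking about barriers that they may be experiencing", followed by the trigger: "If the participant responds to this question, their response will be sent as an auto-notification to the site coordinator". The coordinator then reviews the response and acts as needed. Section 27.2 undertakes to report adverse events to the IRB under the institution's policy.

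Section 15 lists the risks of pumping: "These include low supply, infection, or stressors that can lead to individual's cessation of pumping".

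Section 4.2, where safety endpoints belong, reads: "Individuals may also determine to end study participation based on the recommendation of their primary care physician".

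Section 10 summarises the monthly survey as "changes to lactation practices, current volume, frequency and satisfaction", and section 6 does the same. The Table of Events in 5.2 adds well-being to the monthly and outtake surveys, and 26.1 also lists well-being among the survey data. The sharing table in 5.1 shows a monthly question on ounces expressed with the study pump.

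Other text bears on safety. Section 31.2 describes a question on why pumping stopped, free-text comments, monthly review of volume and frequency, review of early cessation, and a step for safety concerns raised in comments. Section 24.1 has final-survey comments read for alarming content.

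**The concern.** A question about barriers invites answers about what stands in the way of pumping. In this protocol that is mostly the workplace. Section 2.1 sets the usage: "Residents that do not have flexible break times and/or reliable close and secure pumping space face barriers to reaching their lactation goals". The background on residents speaks of the same "barriers as other working mothers (e.g., inadequate space, support, and time". Section 3.3 likewise writes of work barriers as a reason for stopping.

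A participant who treats an infection and keeps pumping may not think of it as a barrier. If she leaves the item blank, no alert is sent. A participant who reports that no room was free does send one. The alert therefore responds readily to the complaint the study is designed to examine, and less reliably to a health event that the protocol foresees.

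Two things are at stake. A participant with a problem may not come to the team's attention promptly. And the study would have no structured count of the one named physical complication, so a small number of reports would say little about how often it occurred. The reporting commitment in 27.2 covers only events that have first been identified.

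**Working it through.** No arithmetic applies: the protocol states no expected event rate, detection rate or safety count. The check sets the named risks against the described means of detecting them.

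**Step 1. Each risk in section 15 against the described survey content (5.1, 5.2, 6, 10, 26.1).**

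| Risk named in section 15 | Described survey item | Linked to the 27.1 alert? |
|---|---|---|
| Infection | None described | Only if volunteered under barriers |
| Low supply | Indirect: monthly volume | No, unless volunteered under barriers |
| Stressors | Indirect: well-being | No, unless volunteered under barriers |

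Volume is an imperfect marker of low supply. The 5.1 question concerns ounces expressed with the study pump, and that figure can also fall through fewer sessions, use of another device, or weaning. No threshold on volume or well-being is stated that would prompt a review.

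**Step 2. The other routes.**

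- *Reason for stopping, and review of early cessation (31.2).* These reach only participants who stop.
- *Final-survey comments (24.1).* These are read at the end of a participant's pumping.
- *Comments and overall data (31.2).* Overall data are reviewed quarterly. Some comments are anonymous, and the response to a safety concern is to ask individuals to notify the team.
- *Monthly review (31.2).* This covers active users, volume and frequency, not health events.
- *Standing of 31.2.* Section 31 is for studies above minimal risk and is marked not applicable, and 27.1 does not refer to it.
- *Departures (25.2).* A participant whose institutional email lapses is removed unless she supplies a new one. No outtake survey is described for her.

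**Step 3. Two cases followed through the text.**

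- *Infection, still pumping, barriers item left blank:* no alert. The reason-for-stopping and early-cessation routes do not apply. The event surfaces only if she writes about it in a comment.
- *No pumping room available, barriers item answered:* alert to the coordinator.

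**Step 4. The safety endpoint.** Section 4.2 grants permission to leave on a physician's advice. It defines nothing that can be counted.

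**The case against.** The best reply is that 27.1 should not be read alone. Sections 24.1 and 31.2 provide further routes, volume is reviewed monthly, and well-being is surveyed. This stands against two stronger readings. A reader might infer that the barriers question is the only way an adverse event can come to light; the documents do not support that. A reader might also infer that none of the section 15 risks is asked about; for low supply and stressors that is wrong, because volume and well-being bear on them. What survives is narrower: the barriers item is the only process 27.1 names and the only one with an automatic alert, and infection alone has no described item.

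A second reply is that barriers can be read broadly. The objectives speak of barriers to lactation goals, section 15 describes its risks as things that can end pumping, and the item sits under adverse-event monitoring. The uses cited above come from objectives and background, not from the survey. This is fair, and some participants will read the question that way. But detection then depends on each participant's reading of one word.

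A third reply is that the forms are attached to the submission and not shown, so the item may already carry health examples. This also stands. The absence of an infection item can be asserted only of the content described, and the consequence is a possibility, not a certainty.

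Finally, this is a minimal-risk study of a marketed device with no aim of estimating infection incidence. That limits the seriousness of the point. It does not remove the need for 27.1 to identify the events it is meant to identify.

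**Conclusion.** The point holds in limited form. Section 27.1 rests adverse-event identification on one voluntary, non-specific question. Of the three risks named in section 15, infection has no described item, and the other two are reached only by data not connected to 27.1. The remaining routes are slower or less specific, and none promptly prompts for an event in someone still pumping. Infection or breast injury may be missed or under-counted.

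The size cannot be derived. A reader might want to put a number on the missed cases, but the documents supply neither an infection risk nor a proportion who would report it as a barrier. Nor do they say that few reports would be taken as proof of minimal risk; that classification is made in advance, in sections 15 and 17.

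The conclusion assumes that the survey summaries reflect the attached forms. If the forms already list these events, what remains is to tie the alert to those items and give 4.2 something measurable. This is an inexpensive safety improvement, not a flaw that undermines the study.

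**What to change.** Keep the barriers item as a study measure. Add one tick-box item to the monthly and outtake surveys, asking whether any of these has occurred since the last survey: breast infection or mastitis; breast or nipple pain or injury; low supply; distress related to pumping; a device problem; none. Trigger the existing coordinator notification from any box other than none.

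Under 4.2, report descriptively the number and proportion of participants with each event. No test or sample-size change is needed.

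Reconcile 27.1 with section 15, the Table of Events in 5.2, section 24.1 and section 31.2, so that 27.1 names every route relied on and the status of the text in section 31 is clear. If the attached survey already lists these events, say so in 27.1 and tie the alert to those items.

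The cost is one REDCap item, a changed alert rule and a minor amendment. Each survey takes a few seconds longer, and the reported event count will rise because events are now solicited. The change affects data collection only and sets no clinical rule.

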## 28.0 Statistical Analysis\*

**28.1** *Describe the data analysis plan, including any statistical procedures or power analysis.*

We plan to examine changes in professional fulfillment and burnout using repeated measures t-test. We also plan to utilize descriptives and qualitative comments to show evidence of whether the Willow device helps the participant reach their lactation goals.

**28.2** *Describe how the sample size for the study was determined (e.g. formal sample size calculation, convenience sampling). To minimize the risks associated with a possible breach of confidentiality, appropriate sample size calculations limit the amount of patient data being recorded to the amount necessary to answer the research question.*

For all the planned analyses, having a study sample of 125-150 will be sufficient. This presents the goal for each site to have 20-25 participants over the next two years.

•
---

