#### 2.2 Hypothesis: *State the hypotheses to be tested.*

Using a wearable breast pump will allow working mothers to continue in their professional obligations and reach their pumping goal.

Secondary: Working mothers' burnout will not increase during the use of wearable breast pump.

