## 4.0 Study Endpoints

### 4.1 *Describe the primary and secondary study endpoints.*

The Individual Participant Endpoint will be at the individuals self-determined endpoint, ideally at the cessation of pumping.

- The study end point will be at the three year anniversary of study start.
- The individuals may also determine to end study participation before they are finished pumping before the 2-year goal.

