## 5.0 Study Design\*

### 5.1 **Study Design:** *Describe and explain the study design.*

Individuals will be given a free Willow device to keep at enrollment with the agreement that in exchange for usage of the device they complete an intake and outtake survey, as well as monthly surveys, to measure goals, experience, and final metrics. They will also consent to Willow and the institution utilizing their mobile app data via their device serial number. This data includes time of using pump, length of use, frequency, and estimated and recorded volumes of pumped milk. Willow will sign the standard research agreement with the understanding that the results from the study are the property of the institution. Data can be pulled by serial number, no identifiers attached. The PIs will not need access to the application data, Willow will share data with the institution at agreed checkpoints. The data will be transmitted via password protected cloud link. Once transmitted the data will be stored on the PIs password protected cloud storage OneDrive.

Data Sharing	Willow to CMKC	CMKC to Willow
--------------	----------------	----------------

SHORT TITLE: Lactation at Work

Serial Number	Via app (User profile)	Via RedCap (project participation (email address) – CMKC team will record device as they are provided to individuals, log them in redcap with their email address, email address blinded in final data
Time (duration of pumping, total minutes) & Frequency (how freq the devices are turned on for use)	Via app	Self-reported via RedCap Survey How many times do you use your Willow pump a day?
Volume (fluid ounces)		Self-reported via RedCap MONTLY Survey (deaggregate) How many ounces to express with your Willow pump a day?
Satisfaction/Goals		Self-reported via RedCap MONTLY Survey (deaggregate) Do you feel like you are meeting your current lactation goals? Which devices are you using to accomplish your lactation goals?

Surveys will be delivered to individuals based on their serial number assignments monthly via redcap for the duration of their pumping experience, devices do not need to be returned to the institution or Willow.

This is a post-market research project targeting students and employees at the institution that have recently given birth and plan to provide human milk for some duration after birth.

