This study will be held over the duration of one year for device distribution and remain open for up to two years or until the last participant indicated completion by completing the endpoint survey.

PI will share results with Willow at agreed upon intervals to provide good faith study data. Results will be shared in de-identified reports with the intent to present at national academic conference in conjunction with two other medical schools that are also delivering this intervention and submission for publication in academic medical journals

Drug/Device Handling: Devices stored in GME or shipped directly to individuals from Willow. No special handling needed for devices, individuals responsible for cleaning and maintenance, devices covered under warranty for first year. (*Products are covered under manufacturer 1 year warranty. All Mom's are asked to contact Willow directly for warranty/troubleshooting and exchange/replacement requests*) Please see our site for in depth warranty information <https://onewillow.com/pages/faq>. Our customer care team number to call is located here with days/times for live help and other avenues of communication to obtain live help. <https://onewillow.com/pages/contact>)

**5.2 Table of Events:** The Table of Events is another helpful tool to present the study procedures in a clear and concise manner. A Table of Events not only helps in the facilitation of IRB review, but is also a useful tool for communicating study details to study staff and even research participants. **It is highly recommended to include a Table of Events for any study involving more than one visit.**

The table below is provided as an example and may be modified as appropriate. The Table of Events must capture the procedures that will be accomplished at each study visit/interaction and all contacts with study participants e.g. telephone contacts. This includes any tests that are used for eligibility, stratification, or decisions on study intervention or discontinuation. Allowable windows should be stated for all visits.

	Intake Survey	Monthly Survey	Outtake Survey
Informed Consent	X		
Delivery of Willow	X		
Demographics	X		

	Intake Survey	Monthly Survey	Outtake Survey
Expectation for Lactation Goals	X		
Previous Lactation Experience	X		
Outcome Evaluation		X	X
Changes to Lactation Goals, practices, current volume, frequency, satisfaction, and well-being		X	X

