## 25.0 Withdrawal of Participants\*inclusio

**25.1** *Describe anticipated circumstances, under which participants will be withdrawn from the research without their consent.*

*A subject can withdraw at any time during the study without being required to return the device.*

**25.2** *Describe procedures that will be followed when participants are withdrawn from the research, including data retention plans or partial withdrawal from procedures with continued data collection.*

*If the subject leaves to the institution (institutional email is deactivated) they will be terminated from the study unless they notify the institution of the transition to remain in the study and provide a new email.*

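### The repeated measures t-test for burnout and fulfillment uses two scores per woman, although well-being is scheduled monthly and the last survey falls at a self-chosen time

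*Protocol*

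**What the plan says.** Section 28.1 names one inferential method: "We plan to examine changes in professional fulfillment and burnout using repeated measures t-test". It does not name the two occasions. The test serves the secondary hypothesis in Section 2.2, that "burnout will not increase during the use of wearable breast pump".

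The data are planned as a series. Section 5.1: "Surveys will be delivered to individuals based on their serial number assignments monthly via redcap for the duration of their pumping experience". The Table of Events in Section 5.2 has a row "Changes to Lactation Goals, practices, current volume, frequency, satisfaction, and well-being", marked under the monthly and outtake surveys but not under intake. Section 26.1 lists well-being among the survey data and says: "We will collect this data via an entry survey, a monthly survey for the duration of pumping, and an exit survey".

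The series has no fixed end. Section 4.1: "The Individual Participant Endpoint will be at the individuals self-determined endpoint, ideally at the cessation of pumping". Section 25.1 adds: "A subject can withdraw at any time during the study without being required to return the device". Section 24.2 lets women skip questions. Under Section 31.2 the outtake survey is sent once a woman reports that she has stopped.

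**The concern.** A repeated measures (paired) t-test reduces each woman to one difference between two values. The schedule produces several values per woman, and their number depends on how long she pumps. If the pair is first score and outtake, three things follow:

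- The differences span unequal lengths of follow-up, so their mean belongs to no stated time after birth.
- Every score in between is left out.
- A woman without an outtake score contributes nothing, even if she answered many monthly surveys.

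The sample is modest and this is the only inferential analysis named, so the cost falls on the one test that the plan commits to. The baseline is also unsettled: Section 26.1 implies a well-being score at entry, and the Table of Events marks none.

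**Working it through.** **The plan's own figure.** Section 28.2 calls 125-150 women sufficient for all analyses. It states no alpha, power, effect size, standard deviation or dropout, so the figure cannot be reproduced. Under an assumed two-sided alpha of 0.05 and 80% power (noncentral t, noncentrality d√n), 125 complete pairs detect a change of d = 0.25 standard deviations of the difference, and 150 detect 0.23. This requires both scores from every woman.

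**When the scores are taken.**

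| Place | Item | Intake | Monthly | Outtake |
|---|---|---|---|---|
| Section 5.2, Table of Events | well-being | not marked | marked | marked |
| Section 26.1 | well-being | implied | implied | implied |
| Sections 6.0 and 10.0, survey lists | neither burnout nor well-being named | - | - | - |
| Sections 2.2 and 28.1 | burnout (28.1 also fulfillment) | no occasion given | no occasion given | no occasion given |

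The monthly survey is described in Section 10.0 only as "changes to lactation practices, current volume, frequency and satisfaction". That burnout and fulfillment belong to the monthly well-being items is therefore an inference.

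**Unequal follow-up.** In the predecessor program reported in Section 3.3, 23 of 41 users (56%) pumped beyond 7 months. The other 18 of 41 (44%) did not. A first-versus-outtake difference would pool these groups.

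**Scores left unused.** With m scores per woman and two used, the unused share is 1 - 2/m. For a linear trend with independent within-woman errors, the slope variance from first and last scores is 2s²/(m-1)², and from all scores 12s²/(m(m²-1)). The ratio is m(m+1)/(6(m-1)).

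| m | Unused | Efficiency of all scores against first and last |
|---|---|---|
| 3 | 33% | 1.00 |
| 4 | 50% | 1.11 |
| 5 | 60% | 1.25 |
| 8 (seven monthly plus outtake) | 75% (6 of 8) | 8×9/(6×7) = 1.71 |
| 13 | 85% | 2.53 |

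**Gain from averaging.** Under equal correlation r, one follow-up minus baseline has variance 2s²(1-r). The mean of k follow-ups minus baseline has s²(1-r)(1+1/k). The ratio (1+1/k)/2 is 0.667, 0.583 and 0.542 for k = 3, 6 and 12, which are reductions of 33%, 42% and 46%. This is the gain from averaging several follow-up scores. A paired test on each woman's follow-up mean would obtain it too.

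**Women without the second score.** The plan gives no rate, so a range is assumed. Start from 125 women and the change detectable with 80% power:

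| Missing second score | Pairs left | Power | Enrolled to keep 125 pairs |
|---|---|---|---|
| 10% | 112 | about 76% | 139 |
| 20% | 100 | about 71% | 157 |
| 30% | 87 | about 64% | 179 |
| 40% | 75 | about 58% | 209 |

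**Simulation (all values assumed).** The set-up was 138 women, seven monthly scores, a true change of 0.30, stopping that depends on the previous observed score, and 200 runs. On average 59% had the last score. The paired test on first and seventh scores had mean 0.296 and standard error 0.115. A linear mixed model with random intercept and slope had mean 0.311 and standard error 0.097. The variance ratio is (0.097/0.115)² = 0.71, about 29% less. The simulated end point was a fixed month, so this shows the precision lost through incomplete pairs and unused scores, not the effect of mixing follow-up lengths.

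**The case against.** The strongest reply is that the surveys themselves are not shown and no section says that burnout is asked monthly. If the scale is given on two occasions only, a paired t-test is natural and nothing is discarded. This stands as a limit on the point. But if burnout is not part of the monthly well-being items, no section schedules it at all, and the planned test has no documented source of data.

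A second reply is that occasions and handling of missing scores are commonly left to a statistical analysis plan. That is fair for those details. The choice of test, however, is made in the protocol.

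Third, start to end of device use is a recognisable target, given the wording of the secondary hypothesis. It is, but its length differs from woman to woman and is chosen by her.

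Fourth, a mixed model does not create scores for women who stop early. It relies on their scores being missing at random. This stands and is met in the fix.

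The documents do not support several stronger readings that a reader might infer:

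- That most of the data are always lost. This holds from about five scores per woman; at four it is half, at three a third.
- That the test will be repeated every month and so inflate false positives. Section 28.1 proposes no such testing.
- That the 33%, 42% and 46% reductions are specific to a mixed model. They come from averaging, which Section 28.1 does not rule out.
- That the paired result would be badly biased. The one simulation run showed both estimates near the true value.

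**Conclusion.** The point holds in a limited form. As written, Section 28.1 commits to a two-score, complete-pair test, while the protocol's own schedule gives repeated well-being scores that end at a self-chosen time. The demonstrated harm is lost precision and an undefined time point. With seven monthly scores plus outtake, 6 of 8 scores go unused. With 10% to 40% missing a second score, an assumed 80% power falls to between about 76% and 58%, part of which a model using the remaining scores can recover.

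The conclusion rests on three assumptions: burnout and fulfillment are among the monthly well-being items, women typically give about five or more scores, and the pair is first score against outtake. The missing rates and simulation values are also assumed. Because this concerns the secondary hypothesis and is easily changed, it is a change that should be made rather than a flaw that invalidates the study.

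**What to change.** 1. In Section 28.1, replace the t-test with a linear mixed model for each outcome. Use all available scores, a participant random intercept and time since birth, with site added if sites are pooled. Keep the paired t-test as a supporting summary.
2. Name one contrast in advance and report it with a 95% confidence interval, for example the mean over months 3 to 6 after birth against the reference score.
3. State which scales measure burnout and fulfillment and at which surveys. Reconcile the Table of Events with Section 26.1 so that a baseline exists. If there is none at entry, add the scale to the intake survey, or use the first monthly score as the reference. The second option is weaker, because Section 7.1 admits women who ask for support only after returning to work, so their first score comes later.
4. State the missing-at-random assumption and add a simple sensitivity analysis, for example shifting the unobserved scores of women who stopped early by a range of amounts. Women who stop before month 3 have no scores in the example window, so this matters for the contrast.

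The cost is small. The biostatistical partner already uses SAS, where the model is standard. Section 7.3 already collects the infant's date of birth and asks the child's age monthly, so time since birth needs no new item. The only possible new data collection is the scale at intake, which would need a revised intake survey.
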